This design allows us to complete the studies at least two days before the next expected menstrual period. Measuring the circadian profile of urinary melatonin over 2 nights for 30+ h will allow us to assess phase, duration and amplitude changes of melatonin reflective of the underlying circadian pacemaker. In addition, we will assess phase-shift responses of melatonin to light in relation to other critical biological rhythm measures of sleep and activity. To document the sleep/wake cycle and exposure to light intensity and spectra, we will use the Actiwatch device (see description below).

[figure not shown]

Figure 1. Study flow: The luteinizing hormone surge (LHS) documents ovulation, c. menstrual cycle day (CD) 14. Urine samples for 6-sulphatoxy-melatonin (6-SMT) and reproductive hormones (RHs) will be collected for 30+ hours over 2 nights between days 8-9 after the LH surge (c. CD 22-23) in months 2,3,5; actigraphy will begin the day of LHS and continue until day 10 after the LHS (CD 14-24) of months 2,3,5; late wake therapy (LWT) or early wake therapy (EWT) will be administered at home on the night of the LHS; bright morning (AM) or evening (PM) light will be administered on days 1-7 after the LHS (CD 15-21) in a counterbalanced, cross-over design in months 3 and 5. Mood ratings (HRSD+BDI) will be collected as follows: Months 1 & 2 – once per week; Months 3 & 5 – LHS + 0 (Pre-

LWT/EWT), daily LHS +1 → LHS + 2 and once the evening after last treatment (LHS +7/8). Visual Analogue Scales (VAS) for depressed mood, anxiety, affective lability, irritability (Daily Mood Ratings)(core PMDD symptoms) collected daily during Months 1 & 2, and twice daily on LHS + 0 through LHS + 2 (for wake therapy effects) and daily LHS + 3 through LH + 10 (for light treatment effects) in Months 3 & 5. HRSD will be collected once during Month 4 and a once a month after Intervention 2 to monitor relapse.

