5. STUDY INTERVENTIONS

5.1 Interventions, Administration, and Duration

Treatment 1 will occur during the menstrual cycle immediately following the 2 menstrual cycles studied in the evaluation period. Washout will occur the following menstrual cycle, and Treatment 2 the menstrual cycle immediately following Washout. As we establish the Evaluation Period as Month 1 and Month 2, we will refer to Treatment 1 as occurring in Month 3, Washout in Month 4, and Treatment 2 in Month 5 (see section 6.1).

During Month 3, qualified participants will sign the Study Consent between cycle days 1 and 10, be randomized to treatment and receive all necessary instructions, forms and equipment to continue with the treatment phase. On the day of their luteinizing hormone (LH) surge (luteal phase), subjects will undergo a night of Late Wake Therapy (LWT) (sleep 21:00-01:00 h, followed by wake) vs. Early Wake Therapy (EWT) (wake until 03:00 h followed by sleep until 07:00 h) at home. We selected the specific wake and sleep times based on our previous work in PMDD.^{36, 37} The following day, subjects will receive the light intervention for 7 consecutive days: days 1-7 after the LH surge (approximately menstrual cycle days 15-21). Depending on their randomization schedule, subjects will receive, at home, 60 min of either AM bright white light (LED of 1350 lux at 20 inches) starting within 30 minutes of their habitual wake time (for those undergoing LWT), or PM bright white light ending 30 min before their habitual sleep onset time (for those undergoing EWT). The following Month 4 (Washout) will be a month of no intervention to prevent any carry-over effects from the Month 3 intervention affecting measures in Month 5. Mirroring Month 3 timing, in the luteal phase of Month 5, subjects will receive the alternate wake therapy (LWT or EWT) and light exposure (AM or PM) (see Fig. 1, above).

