9.5 Outcomes

9.5.1 Primary Outcome

- Treatment-Related Mood Rating Changes from Baseline (month 2) to post intervention (months 3,5) :
Mood ratings include Hamilton Rating Scale for Depression (HRSD), Beck Depression Inventory (BDI), atypical depression symptoms as part of the Structured Interview Guide for the Hamilton Depression Rating Scale, Seasonal Affective Disorders version (SIGH-SAD), Beck Anxiety Inventory (BAI), mania ratings, the Psychological General Well-Being Index (PGWI) and daily mood self-ratings (DMR) that include core PMDD symptoms of anxiety and irritability as required during diagnostic evaluation, before, during and after each wake and light intervention at the same time of day (between 15:00-17:00 h). To assess more acute effects on mood that may occur more rapidly during the wake interventions, subjects will complete DMRs twice daily beginning the evening before the wake therapy intervention and continuing until the morning after the recovery night of sleep.
- Treatment-Related Urinary 6-sulfatoxymelatonin (6-SMT) Changes from Baseline (month 2) to post intervention (months 3,5) :
6-SMT is a principal melatonin metabolite that is abundant in urine, well correlated with plasma melatonin, and serves as an excellent marker for circadian phase response.
- Treatment-related changes in objective and subjective sleep measures:
Using actigraphy, we will obtain objective measures of the sleep/wake cycle to ensure appropriate sleep/wake times during wake therapy, and during the light interventions as it is an important biological rhythm with which to compare the intervention-induced melatonin rhythm changes. To assess subjective sleep quality, we will use the Pittsburgh Sleep Quality Index (PSQI) and a visual analogue scale.

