Actiwatches: Activity and illumination will be examined to determine time-in-bed and any naps that occur during the day. Daily total sleep time, wake time, number of awakenings and distribution of lengths of awakenings for night and day separately in each 24 h period will be determined using the automated sleep-wake scoring algorithm and custom SAS procedures that we have developed.⁷⁰ Extended cosinor analyses⁷⁰ will be done to determine the mesor, amplitude and acrophase of activity and illumination and the f-statistic (with higher values representing more robust and synchronized rhythms that we expect to correlate with improved mood). The mean and maximum light intensities (in lux) and the number of minutes above 1,000 lux

also will be examined. Analyses then will be done comparing activity, sleep and light exposure between groups and time of light intervention with the light and activity summary variables as continuous covariates. Baseline pre-intervention values and post-intervention activity and illumination values also can be compared for a specific light pulse. These analyses will determine if the following variables predict the magnitude of treatment and phase-shift responses: 1) The timing of activity onset and offset, 2) The amplitude of activity at baseline, 3) The illumination levels at baseline.¹ For young adults, the Actiwatch is an accurate method for recording both the in-bed interval and for estimating the time asleep.⁷¹ Although presumably less accurate on a nightly basis than PSG, the Actiwatch is capable of several weeks of round-the clock recording, which would not be feasible with PSG either in the CTRI or at home.

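### Section 9.6 adjusts the AM–PM comparison of actigraphic sleep, activity and light for light and activity summaries without limiting those covariates to the Month 2 baseline

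*Combined protocol and SAP*

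**What the plan says.** The Actiwatch paragraph of Section 9.6 defines its summary variables first. Extended cosinor analysis is used to "determine the mesor, amplitude and acrophase of activity and illumination and the f-statistic". It then adds "The mean and maximum light intensities (in lux) and the number of minutes above 1,000 lux". The next sentence gives the treatment comparison: "comparing activity, sleep and light exposure between groups and time of light intervention with the light and activity summary variables as continuous covariates". It names no month for the covariates.

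A little further on, the paragraph states a predictive purpose: "These analyses will determine if the following variables predict the magnitude of treatment and phase-shift responses". Three predictors follow. Activity amplitude and illumination level are tied to baseline; the timing of activity onset and offset is not.

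The recording window is in the Figure 1 legend of Section 3: "actigraphy will begin the day of LHS and continue until day 10 after the LHS (CD 14-24) of months 2,3,5". Section 9.5.1 lists "Treatment-related changes in objective and subjective sleep measures" among the primary outcomes, and Section 1.1 includes sleep and activity in the primary objective.

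**The concern.** What is randomised is the order of two treatments that differ in the timing of wakefulness and light. A light or activity summary recorded in Month 3 or 5 is measured after randomisation and partly records the treatment. Adjusting for it changes the question from what the two treatments do to sleep, to what they would do if light timing or activity did not differ between them. For the activity and light outcomes, the same quantity could stand on both sides of the model.

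Two features raise the stakes. The trial's premise is that timing is the active ingredient, so an effect passing through light timing is what the protocol itself expects. And this sentence is the only stated between-treatment analysis of actigraphic sleep. The random regression model is assigned to hypothesis 1.A (mood), sleep logs are compared before versus after, and PSQI is handled separately. If the covariate period stays open, it can also be chosen after the data are seen.

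**Working it through.** The documents give no effect size, variance or power for actigraphic sleep, so there is no stated figure to reproduce. The check has three steps; steps 2 and 3 rest on labelled assumptions.

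**Step 1. What the recordings contain.** Recording runs from the LH-surge day to day 10 after it. Wake therapy falls on the surge night and light on days 1–7. A Month 3 or 5 summary therefore spans the whole intervention. A Month 2 summary covers the same cycle window with no intervention.

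**Step 2. Which light summaries differ between treatments by construction.** Section 5.1 gives "60 min of either AM bright white light (LED of 1350 lux at 20 inches", or the same device for the same time in the evening. The study-light dose is equal; its clock time is not. A 60-min pulse of 1,350 lux was added at 07:15 or 21:30 (assumed times) to three assumed ambient profiles, with these results:

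| Summary | AM versus PM |
|---|---|
| Mean lux, maximum lux, illumination mesor | identical |
| Minutes above 1,000 lux | 60 in each |
| Illumination acrophase, log10 lux | differs by 0.33–0.37 h |
| Illumination acrophase, linear lux | differs by 1.7–5.1 h |

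This used a single cosinor, not the extended cosinor in the plan. It shows which summaries separate the treatments; it does not predict the size of the shift. Activity summaries are a separate case: sleep is inferred from wrist activity, so same-period activity is the signal from which the outcome is scored.

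**Step 3. What adjustment does.** Let d be a woman's AM-minus-PM sleep difference and m her AM-minus-PM difference in on-treatment acrophase, with mean D. Let T be the total effect and p the share that runs through m:

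d = (1 − p)·T + (p·T/D)·m + error.

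Without adjustment, the mean of d estimates (1 − p)·T + p·T = T. With m as covariate, the treatment effect is the intercept at m = 0, which is (1 − p)·T.

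Assumed inputs: N = 40 pairs (the planned number), T = 0.50, error SD 1, D = 1 h, acrophase SD 0.75 h within each treatment period, two-sided t test at 0.05, 4,000 runs per row.

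| Share p | (1 − p) × 0.50 | Simulated adjusted estimate | Power unadjusted | Power adjusted |
|---|---|---|---|---|
| 0% | 0.500 | 0.50 | 0.87 | 0.60 |
| 25% | 0.375 | 0.38 | 0.86 | 0.40 |
| 50% | 0.250 | 0.25 | 0.84 | 0.20 |
| 75% | 0.125 | 0.13 | 0.82 | 0.08 |
| 100% | 0.000 | 0.00 | 0.79 | 0.04 |

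In the 0% row nothing is lost from the estimate, but its standard error rises from 0.16 to 0.22. With D = 0.5 h the rise is from 0.16 to 0.18, so the precision cost depends heavily on D. Replacing m with a Month 2 covariate (p = 50%) gives 0.50, with power 0.84 both with and without it.

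**The case against.** The strongest reply is that the authors meant Month 2 values. Month 2 actigraphy exists over the same window, the paragraph's stated purpose is prediction, and two of its three predictors are baseline values. On-treatment covariates also make the sentence degenerate for light and activity, whereas Month 2 covariates make it ordinary baseline adjustment. This stands as far as it goes: the period is unstated, and the text does not show that on-treatment values are intended. But the authors write the baseline limit where they want it, and this sentence lacks it.

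Second, most of the light summaries are not the AM–PM contrast. That also stands. With equal study-light dose, mean lux, maximum lux and minutes above 1,000 lux need not differ. The concern is confined to timing summaries and activity summaries.

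Third, hypothesis 1 states no AM–PM effect on actigraphic sleep and uses sleep as a reference for melatonin timing; Section 9.6 also allows a comparison of baseline and post-intervention activity and illumination with no covariate named. This does not dispose of the point. Sections 1.1 and 9.5.1 make sleep a primary matter, and the unadjusted option covers activity and illumination, not sleep, and compares before with after, not AM with PM.

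A reader might infer that the plan adjusts the primary sleep effect away, or that the standard error will be inflated several-fold. The documents support neither. Both depend on the covariate period, the mediated share, the ambient light and the spread of acrophase, none of which they give.

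**Conclusion.** The point holds as a fault of specification. The sentence sets a rule for comparing a listed primary outcome between treatments, and the rule admits covariates that record the intervention. Under on-treatment values, the loss from the actigraphic sleep effect equals the share passing through the covariate, anywhere from 0% to 100%. Under Month 2 values it is nil. That range follows from the linear model; the power figures and the acrophase shifts are illustrations on assumed inputs.

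The scope is limited to the actigraphic comparisons of sleep, activity and light. No light or activity covariate is named for mood, 6-SMT, PSQI or the sleep VAS, so those analyses are not affected.

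**What to change.** In Section 9.6, replace the comparison sentence with wording to this effect:

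*Sleep, activity and illumination recorded in Months 3 and 5 will be compared between LWT+AM BWL and EWT+PM BWL within woman. Only Month 2 light and activity summaries may enter as covariates or predictors. Light and activity recorded during treatment will be reported as exposure and adherence; any model that adjusts for them will be labelled exploratory mediation.*

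Add the Month 2 limit to the one listed predictor that lacks it, the timing of activity onset and offset. The change should be made before treatment-coded actigraphy data are examined. It costs a few lines of text and needs no new data, visits or participants.

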6.2.4 Treatment Visits

In accordance with the Schedule of Evaluations (section 6.1 above), treatment-related measures will be collected in months 3 and 5 as follows:

- Hamilton: The Hamilton Rating Scale for Depression (HRSD)⁵⁶ (as a validated objective, interview-based assessment of depression). Atypical depression symptoms as part of the Structured Interview Guide for the Hamilton Depression Rating Scale, Seasonal Affective Disorders version (SIGH-SAD)⁶⁰ (as atypical symptoms in particular respond to light treatment⁶¹) Mania⁶² ratings (to document any clinical induction of manic symptoms by the wake or light interventions) – on ovulation night (LSH), daily on LHS+1 – LHS+2 (during intervention) and once after light treatment on LHS+8-9 (post-intervention assessment).
- Beck Depression Inventory (BDI)⁵⁷ (as a validated subjective assessment of depression) – on ovulation night (LSH), daily on LHS+1 – LHS+2 (during intervention) and once after light treatment on LHS+8-9 (post-intervention assessment),
- Beck Anxiety Inventory (BAI)⁵⁸ (as many women with PMDD report anxiety symptoms)⁶³ – on ovulation night (LSH), daily on LHS+1 – LHS+2 (during intervention) and once after light treatment on LHS+8-9 (post-intervention assessment),
- The Psychological General Well-Being Index (PGWI)⁶⁴ – on ovulation night (LSH), daily on LHS+1 – LHS+2 (during intervention) and once after light treatment on LHS+8-9 (post-intervention assessment),

- Daily mood self-ratings (DMR)⁵⁴ that include core PMDD symptoms of anxiety and irritability – collected daily on LHS+0 through LHS+2 (for wake therapy effects) and daily LHS+3 through LHS+10 (for light treatment effects),
- Pittsburgh Sleep Quality Index (PSQI)⁶⁷ to assess subjective sleep quality – once on LHS+8-9 (post-intervention assessment),
- Visual analogue scale⁶⁸ to assess subjective sleep quality – once on LHS+8-9 (post-intervention assessment),
- Ovulation testing performed for 7 days starting on menstrual cycle day 10 in months 3 and 5 to determine luteinizing hormone surge (LHS). Participants will contact Study Coordinator with their time of first menses (cycle day 1) to determine cycle day 10 and schedule appointment for collecting study forms and equipment,
- Actigraphy will be collected for 10 days starting the day of LHS to monitor baseline sleep, light and activity measures at home,
- Urine collection for 30 hrs performed between days 8-9 after LHS.

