9. STATISTICAL CONSIDERATIONS

9.1 General Design Issues

The design is a randomized cross-over contrasting LWT+AM bright light vs. EWT+PM bright light administered in the luteal phase of two separate menstrual cycles, and preceded by 2 evaluation months. To lessen the patient's burden, the 1-night EWT or LWT and the following 7-day BWL interventions will be conducted at home, given at a fixed point in each menstrual cycle, from day 1 to 7 after the mid-cycle LH surge. We anticipate that LWT+7 days of AM BWL (vs. EWT+PM BWL) will produce much greater mood benefits and larger physiological responses, than the one-time light pulses used in our earlier phase-shift studies.

The wake therapy and light interventions proposed in this application are based on our previous studies in PMDD and key published experiments by other investigators that indicate that the combined interventions are efficacious in other mood disorders after one week of treatment and maintained at 9-months follow-up. To provide optimal timing of interventions, we will administer wake therapy in the early-night vs. late-night and light pulses in the AM vs. PM at selected times in relation to sleep (within 30 min of waking and 90 min before sleep onset, respectively).

A crossover treatment design is employed to compare LWT+AM BWL vs. EWT+PM BWL responses within the same individual. As wake interventions lose effectiveness after 1 day, and light treatment effects after 3-4 days, we anticipate minimal carry-over effects of the wake plus light interventions administered a month apart. To further ensure no carry-over effects, there will be a month of no-intervention between the 1st and 2nd treatments. Because our previous studies clearly indicated differences between PMDD and NC subjects occurred primarily in the luteal menstrual cycle phase, we will treat during this menstrual cycle phase rather than in the follicular phase.

Hypothesis (H) 1: For PMDD patients in the luteal phase, LWT+AM BWL, compared with EWT+PM BWL, will A) Decrease scores on SIGH-SAD, BDI, BAI, and DMR, and increase global assessment of treatment effectiveness from baseline to post-intervention; B) Phase-advance urinary melatonin timing measures (acrophase, onset and offset time) in relation to clock time and to sleep measures (onset, end time and mid-sleep times); C) The magnitude of the phase-advance (B, above) will correlate with the magnitude of the symptom changes (A, above) by linear regression.

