9.2 Sample Size and Randomization

For our primary outcome measures of mood, based on our earlier data reflecting

seven days of light exposure alone² (i.e., without the ‘priming’ effect of wake therapy), we predict the following changes in mood in PMDD subjects (N = 40) after Late Wake Therapy plus AM Light vs. Early Wake Therapy plus PM Light: A significantly greater improvement (decrease in raw score) will be detected at the p = .05 level with (a) 71% power in Hamilton Rating Scale for Depression (HRSD) Score (Mean difference 3.15±9; effect size = .324); (b) > 99% power in atypical score (Mean difference 4.45±5; effect size = .78); (c) > 99 % power in Structured Interview Guide for the Hamilton Depression Rating Scale, Seasonal Affective Disorders (SIGH-SAD) Items (Mean difference 7.0±11; effect size = .627); (d) 86% power in Beck Depression Inventory (BDI) score (Mean difference 6.30±15; effect size = .378).

For the recovery criterion of $\geq 50\%$ decrease from baseline (Chi Square analyses): (a) 97% power for HRSD score (difference in proportions: .44); (b) 70% power for atypical score (difference in proportions: .30); (c) 86% for SIGH-SAD score (difference in proportions: .325); and (d) 93% power for BDI score (difference in proportions: .40). For the remission criterion of reduction to a score of ≤ 8 (Chi Square analyses): (a) 89% power for the SIGH-SAD score; (b) 44% power for the BDI score. All tests are two-tailed.

We also performed power analyses for the primary hypotheses, incorporating the longitudinal nature of the design for the proposed Random Regression model (also known as Multilevel Models, or Growth Curve Models). Procedures describes by Hedeker et al.⁶⁹ for Random Regression Models, with the above data, was used for the proposed study to estimated needed sample size. We assume a Type-I error level (alpha-level) of 0.05, drop-out rate of 10% to 15% and an autoregressive covariance structure, with correlation between sequential assessments set at 0.45 (based on our previous data). We are confident based on our results from these two separate approaches that the proposed study will have minimum power of 80% to yield a statistically significant result for a medium effect size. Here, medium effect size is defined as a treatment difference increasing linearly from 0 at baseline to .5 SD units at the last time point. Type 1 error will be controlled by correcting the p-value per domain.

Treatment Assignment Procedures

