Specifically, data for hypothesis 1.A. will be analyzed using a Random Regression Model (RRM), a generalized linear model described by Gibbons et al.,⁷⁴ Hedeker et al.⁶⁹ and Laird.⁷⁵ The random effects method has several advantages over more traditional analytic approaches such as a change score, end-point or repeated measures analysis of variance. This method allows the inclusion of subjects with missing data or those who were terminated early in the study, without relying on data imputation procedures. This method provides an estimate of the individual variability around the population trend, the variability of the individual intercepts (baseline values) and slopes (changes across time), and the correlation between them. A fully saturated treatment by time model will be utilized for inference. Co-variance structure will be chosen based on Akaike's Information Criterion (AIC). Random treatment effects also will be evaluated for importance based on the model AIC. This plan allows for any group level effects to be incorporated into the model. Denominator degrees of freedom will be calculated using the Kenward-Roger small sample correction. All subjects will be included in the analyses, and we will not focus only on subjects who complete the study. Our methods for data analyses include all subjects with any valid data points in the analyses. Secondary analyses will be performed on data from completers. Type 1 error will be controlled by correcting the p-value per domain. For hypothesis 1.B, an individual's slope for each of the dependent variables listed above will be calculated and will be used for correlational analysis using the Pearson method. In addition, we will examine the number of responders. The operational definition of the criteria for

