response on the mood measures, the HRSD, SIGH-SAD and the BDI, is a decrease of > 50% in the pre-treatment/baseline score, while the remission criterion will be a decline to a value < 8 on the SIGH-SAD and BDI as per Terman et al.⁴¹ We will compare percentages of PMDD subjects achieving the Terman criteria in groups receiving different interventions using Chi Square analysis. Results from Expectation Forms and Horne-Ostberg Scales will be examined in relation to the magnitude of mood change after interventions as assessed by mood ratings, the Psychological General Well-Being Index (PGWI), and side effects checklists. We also will examine the effect of diagnosis and light intervention on measures of subjective sleep quality as measured by the Pittsburgh Sleep Quality Index (PSQI), and differences between groups or intervention on outcome measures as a function of the phase-angle difference (PAD) between melatonin timing (acrophase, onset, offset) and sleep (onset, end-time, mid-sleep) measures. Data for hypothesis 1.C will be analyzed similar to hypothesis 1.B. Data for hypothesis 2.A will be analyzed similar to hypothesis 1.A using RRM. Data from LWT + AM BWL, however, will be used only. Data for hypothesis 2.B will be analyzed similar to hypothesis 1.B by using individual slope in the correlational analysis. Data for hypothesis 3.A will be analyzed similar to hypothesis 1.B, and for hypothesis 3.B, similar to hypothesis 1.A using only EWT +PM BWL treatment data.

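### The responder Chi Square treats the same women as two independent groups, and the crossover mood model names no period term

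*Combined protocol and SAP*

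**What the plan says.** Sections 6.2.2 and 9.1 describe a two-period crossover: each woman receives one combined intervention in month 3 and the other in month 5, with sequence allocated 1:1.

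For hypothesis 1.A, Section 9.6 specifies a random regression model and states: "A fully saturated treatment by time model will be utilized for inference". Covariance structure and random treatment effects are chosen by AIC, with Kenward-Roger degrees of freedom. No period or sequence term is named. The nearest wording is general: "This plan allows for any group level effects to be incorporated into the model".

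Section 9.6 then adds a responder analysis for HRSD, SIGH-SAD and BDI. Response "is a decrease of > 50% in the pre-treatment/baseline score", and remission is a low score on SIGH-SAD or BDI. The percentages under the two interventions are compared by Chi Square, with the women described as groups. No paired method is named.

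On time and baseline, Section 9.2 powers "a treatment difference increasing linearly from 0 at baseline to .5 SD units at the last time point", which reads as occasion within a course, while Section 9.6 lists study months 3 to 6. Section 9.5.1 defines the primary outcome as "Treatment-Related Mood Rating Changes from Baseline (month 2) to post intervention (months 3,5". Section 6.2.4 also schedules mood ratings in each treatment month "on ovulation night (LSH), daily on LHS+1 – LHS+2 (during intervention) and once after light treatment on LHS+8-9 (post-intervention assessment".

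**The concern.** A crossover is chosen so that each woman serves as her own control. The ordinary Chi Square discards that pairing and computes its standard error as if 80 different women had been studied. Its nominal 5% level is then wrong, and it gives up power in a 40-woman trial.

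The mood model raises a related question. Scores may differ between month 3 and month 5 for reasons unrelated to treatment. The washout month addresses carry-over, not a shift of this kind. Without a period effect the shift stays in the within-woman difference: as extra variance when sequences are balanced, and partly as bias when they are not.

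**Working it through.** **Inputs.** From Section 9.2: N = 40; two-tailed alpha .05; HRSD difference 3.15 with SD 9; planned differences in response of .44 (HRSD), .325 (SIGH-SAD) and .40 (BDI). Assumed, because the documents do not give them: the response rate on the poorer treatment, the within-woman correlation and the size of any period shift.

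**The plan's own figures.** The stated HRSD power is 71%. A two-sided paired t test gives .579 at 3.15/9 = .35, or .515 at the printed effect size of .324, so 71% is not reproduced. That is a separate matter; .579 is used below only as a starting point. The responder powers (97% HRSD, 70% atypical, 86% SIGH-SAD, 93% BDI) cannot be confirmed because the lower proportions are not stated. All four can be matched by an unpaired, continuity-corrected test with 40 per condition, for lower proportions of .10–.46, .25–.45, .10–.15 or .53–.57, and .18–.42 respectively. With 20 per group, HRSD, SIGH-SAD and BDI cannot be matched. This supports reading the test as unpaired.

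**Chi Square, Type I error.** Under the null the test assumes Var(p1 − p2) = 2p(1−p)/n. With within-woman correlation φ between the two binary outcomes, the true variance is 2p(1−p)(1−φ)/n. The approximate Type I error is therefore 2[1 − Φ(1.96/√(1−φ))]:
- φ = .2: 1.96/.894 = 2.19, giving .028
- φ = .45: 1.96/.742 = 2.64, giving .008
- φ = −.2: 1.96/1.095 = 1.79, giving .074

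Simulating correlated normal variables cut at the response threshold (rates .2–.4, latent correlation .3–.6, which corresponds to a smaller φ) gives .011–.035 for the uncorrected test and .004–.016 with continuity correction. The documents do not say which is meant.

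**Chi Square, power.** Same simulation, uncorrected test, against a period-adjusted within-woman t test (38 df):

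| Outcome (difference) | Chi Square | Within-woman | Loss, points |
|---|---|---|---|
| SIGH-SAD (.325) | .88–.92 | .91–.97 | 2–6 |
| BDI (.40) | .976–.989 | .982–.998 | about 0.5–1 |
| HRSD (.44) | .993–.997 | .995–1.00 | under 0.5 |

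**Period shift, balanced sequences (20/20).** Take time as occasion within a course, and the outcome as change from a shared month-2 baseline or as the post-treatment level. With month-3-minus-month-5 shift s, the expected within-woman difference is τ + s in one sequence and τ − s in the other. Without a period term the variance is 9² + s², and the noncentrality is 3.15√40/√(81 + s²) = 19.92/√(81 + s²), with 39 df:

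| s | Noncentrality | Power | Type I error |
|---|---|---|---|
| 0 | 2.21 | .579 | 5.0% |
| 1 | 2.20 | .574 | 4.8% |
| 2 | 2.16 | .559 | 4.5% |
| 3 | 2.10 | .535 | 3.9% |
| 5 | 1.93 | .471 | 2.5% |

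With a period term (38 df) power is .578 whatever s is.

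**Period shift, unequal completers.** Bias is s(n1 − n2)/40. At 24/16 it is 0.2s: 0.6 points at s = 3 and 1.0 at s = 5, with simulated Type I error of about .056 and .062. At 22/18 it is 0.1s, or 0.3 points at s = 3, and Type I error is .042. A period term brings bias to 0 and Type I error to about .05.

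**Where the shift drops out.** If change is taken from each course's own LH-surge-night rating, a shift common to both ratings cancels. Only a shift that differs between that night and LHS+8-9 remains.

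**The case against.** Several points on the other side stand. Sequences are randomized 1:1, so with random drop-out the omitted period effect causes no bias on average. The documents give no evidence of a shift, and its cost is small up to 2 points. The sentence on group-level effects permits a period term. If time were coded as study month, a saturated model would already absorb period, although the tested contrast would then have to be named, since treatment by month is the sequence or carry-over contrast. The responder analysis is supplementary to the mood model.

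A reader might go further than the documents allow in five ways:
- *The Chi Square produces false positives.* With positive within-woman correlation it is conservative; it becomes anti-conservative only if the correlation is negative.
- *The power loss reaches 8 or 9 points.* That needs the .30 difference, which Section 9.2 gives for the atypical score. Section 9.6 does not define response on that score.
- *Omitting period never inflates Type I error.* That holds for balanced sequences but fails at 24/16.
- *The missing period term explains why 71% power is not reached.* It does not: .579 already assumes no shift.
- *The baseline is undefined.* Sections 6.2.1, 6.2.2 and 9.5.1 place it in month 2. What is unstated is which of that month's weekly ratings, follicular or luteal, are used.

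**Conclusion.** The concern holds in two parts. The firmer one is the responder test: a stated analysis relies on independence that the design rules out. Its Type I error is about .011–.035 (.004–.016 with continuity correction) instead of .05, under assumed response rates of .2–.4 and latent correlations of .3–.6. The power lost by the uncorrected test is modest for SIGH-SAD and slight for BDI and HRSD. This part needs no period shift.

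The second part is an omission rather than a wrong formula. The mood model permits a period term but does not commit to one. If time is occasion within a course and a shift exists, balanced sequences cost power only. A marked imbalance such as 24/16 adds bias of 0.2 points per point of shift and a small excess in Type I error. The shift sizes and that split are assumptions. Time coding and the choice of month-2 rating are matters of missing detail.

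**What to change.** In Section 9.6:

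(a) Replace the Chi Square for response and remission with a paired, period-adjusted analysis. One option is a single mixed model of the 0/1 outcome with random woman, treatment and period; another is a within-woman period-adjusted test. Take the estimate and the p-value from the same model.

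(b) Define time as rating occasion within a course. Add fixed period (month 3 or 5) and period-by-time terms to the random regression model, and name the post-intervention treatment contrast averaged over periods as the test. The period-by-time term is needed because PMDD symptoms are late-luteal by the criteria in Section 4.3, so a shift may appear at LHS+8-9 but not on the LH surge night.

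In the same edit, state which month-2 luteal rating or ratings form the baseline. This is a clarification, not the correction of an error.

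The cost is a few sentences and no new data. At the post-intervention rating the period adjustment takes 1 df: power is .578 instead of .579 if there is no shift.
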